#### 1) Objectives\*

Our overall hypothesis is that tunneling wound (TW) formation is key in disease progression from local skin disease to systemic inflammatory disease. Further we hypothesize that biofilms present in the TW are detrimental to healing and allow propagation of the disease process. Our specific hypotheses for this project are: H1: Biofilms exist in HS TW, as determined by microbiome identification and enumeration

H2: antibiofilm treatment can resolve biofilms in HS TW, as determined by microbiome identification and enumeration, histology, or inflammatory and antimicrobial tissue response by host gene expression

H3: treatment of the biofilms in TW modulates the systemic host response.

# 2) Background\*

Hidradenitis Suppurativa (HS) is a devastating chronic skin disease affecting approximately 1% of the population. Currently, there is no cure for HS. Standard care includes combination of medical and surgical therapies. There is only one agent tested in RCT which provides moderate relief to about half of the patients. As part of disease progression, dermal and subcutaneous tunneling wounds (TW) that communicate with the skin's surface form and are colonized with bacteria. Emerging evidence suggests biofilms form in the TW of HS. Tunnel formation occurs when patients go from locally contained disease to having systemic inflammatory disease and symptoms. While it is generally believed that the skin microbiome participates in the pathogenesis of HS, the presence and the role of biofilms in the cutaneous tunnels has not been well characterized. Additionally, if biofilms exist, eradication of biofilms in the TW may improve HS. We have reported our anecdotal success with treatment of HS TW with antibiofilm surfactant wound gel (ABWG,) (in submission) and we aim to prospectively examine the mechanisms involved.

#### 3) Inclusion and Exclusion Criteria\*

Inclusion criteria

- 1. Adults 18 years old and older
- 2. Have diagnosis of HS confirmed by a dermatologist

- 3. Have at least one HS related tunneling wound that is at least 2 CM in length
- 4. Able to provide informed consent

#### Exclusion criteria:

- 1. Individuals who are not yet adults
- 2. Women known to be pregnant
- 3. Prisoners
- 4. Subjects, who in the opinion of the PI, cannot comply with home application of the treatment.

# 4) Number of Subjects\*

We intend to recruit 15 subjects.

#### 5) Study-Wide Recruitment Methods\*

Patients with HS seen for their routine care at the Dermatology Outpatient Clinics at the University of Miami Hospital, South Miami satellite site, or Lennar Medical Foundation satellite site will be identified for possible study eligibility by any of the dermatologists in our practice. If the treating dermatologist is a study team member, they will ask the potential subject if they would be interested in being contacted by the study team to learn more about a research study for HS. A partial HIPAA waiver is needed, so that if the patient gives permission to be contacted, they will then be approached by a member of the study team while they are in clinic or if that is not feasible then the treating dermatologist will ask if the patient would like to be contacted by telephone. If the treating dermatologist is not a study team member, they will ask the potential subject to contact the study team for more information by providing the study team's contact information and/or the study flyer. If the potential subject agrees to be contacted by the study team, the treating physician will ask the patient to sign a PHI release authorization form, so that the physician can provide the study team the patient's contact information. If it is then determined that they are interested in participating, they will be scheduled for a visit with the PI at our University of Miami Hospital dermatology clinic site where informed consent and all other study procedures will take place. The risks/benefits of the study will be presented to the subjects, as well as the disclaimer that refusal to participate in the study will in no way, shape, or form alter the type or quality of their care.

A partial HIPAA waiver is also needed as patients diagnosed with HS who signed the University of Miami's Consent to Contact consent during their routine medical care will be identified using research IT and URIDE. Each of those individuals with then be contacted by the phone by a study team member and asked if they would be interested in learning more about a research study on HS. If it is then determined that they are interested in participating, they will be scheduled for a visit with the PI at our

University of Miami Hospital dermatology clinic site where informed consent and all other study procedures will take place. The risks/benefits of the study will be presented to the subjects, as well as the disclaimer that refusal to participate in the study will in no way, shape, or form alter the type or quality of their care.

# 6) Study Timelines\*

We intend to enroll subjects over a one-year period from the date of IRB approval. Each subject will participate in the study for a total of 4 weeks (28 days +/- 3). Each subject will be invited for 3 visits: initial visit, follow up visit and final visit.

#### 7) Study Endpoints\*

The primary endpoint of the study is the change in microbiome from HS TW before and after 4 weeks treatment with the ABWG as measured by quantitative 16s rDNA PCR for bacterial enumeration.

Secondary outcomes include: Change in lesion severity (as measured by HS-PGA (Table 1) and Hurley Stage (Table 2)), change in pain from baseline (as measured by a 100 mm visual analogue scale), change from baseline in HS lesion erythema as measured by the Clinical Erythema Assessment (CEA) scale (Table 5), change from baseline in exudate graded from none to leaking (see Table 4), changes from baseline in range of motion as measured by a goniometer in the following directions: flexion, extension, abduction, internal and external rotation (Table 6), change in quantity and type of pain medication use, weekly change in number days of work/school lost, number of dressing used per week, Quality of life (using HiSQOL and DLQI).

Other descriptive measures included:

- Microbiome assessment from the tissue using metagenome shotgun sequencing approach to identify all species and their corresponding virulence factors, including genes responsible for biofilm formation antibiotic resistance genes, etc.
- Tissue assessment by histology
- Inflammatory and antimicrobial tissue response by host gene expression before and after treatment for ten representative genes.
- Confocal laser scanning microscopy to visualize and confirm biofilm before and after treatment will be performed on a small subset of subjects (about 5)
- Change from baseline in serum levels of markers of inflammation such as IL-6, IL-8, IL-10, IL-17α, soluble TNF receptor II (sTNF-RII), C-reactive protein (CRP) and erythrocyte sedimentation rate (ESR).

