# 8) Procedures Involved\*

After informed consent is obtained from each subject, they will be invited to participate in the study for 3 visits over 4 weeks. The procedures involved are listed in the table of assessments.

Week	0	+2	+4
Visit	V1	V2	V4
Window (days)	0	±3	±3
Informed consent	X		
Eligibility	X		
Subject ID assignment	X		
Chart review	X		
Demographics	X		
HS history	X		
Medical history	X		
Concomitant medication	X	X	X
Physical exam (focused)	X	X	X
HS lesion map	X X X X	X X X	X
HS lesion ultrasound	X	X	X X X
Hurley stage	X	X	X
HS-PGA	X	X	X
Pain (VAS) -General	X	X	X
Pain (VAS) -target TW	X	X	X
Pain medication usage	X	X	X
past 3 days		Λ	Λ
Height	X		
Body weight	X		X
Exudate	X	X X	X
Erythema	X	X	X
Range of motion affected joint	X	X	X
Incision and drainage	X		
Product application	X	X	X
Tissue collection	X		X
Serum collection	X		X X
QOL	X		X
Work/school days lost	X	X	X
Number of dressing used	X	X	X
Photography	X	X	X
Ease of ABWG	i		
application	X	X	X
Adverse events	X	X	X

At the first visit, the medical history will be reviewed and demographics, HS history and concomitant medications will recorded using the medical chart and history given by the patient. Then, the tunnel of interest will be identified and a picture of the lesion will be taken. The first swab of the lesion will be performed and placed in a collection tube labeled with the patient number, date and "pre." The area will be cleaned, then anesthetized using local anesthesia. Once the area is properly anesthetized, a punch incision will be made and the tissue placed in a sterile petri dish lined with gauze labeled with the patient number, date and 1. After the tissue is place in the dish, sterile PBS will be added to the gauze.

A probe will then be inserted into the tunnel to identify the terminal end. A second punch incision will be made at the end of the tunnel and the tissue will be collected in a second sterile petri dish labeled with the patient number, date and 2. Hemostasis will be achieved. Once hemostasis is achieved, a second picture will be taken of the lesion. The ABWG (BlastX, NextScience, Jacksonville, FL) will then be applied to both punch sites using a tongue depressor. Absorbent dressing will be applied to cover the wound.

In the days between visits, patients will apply one fingertip unit of the ABWG to the study wound daily.

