In order to correlate the change in microbiome to secondary clinical outcomes, at each visit a focused physical exam will be performed. The corresponding HS-PGA (Table 1) and Hurley Stage (Table 2) will be calculated. The HS lesion locations will be marked on a HS Lesion Body Map (Table 3) and will also be photographed using standard photography.

At each visit, the subject's pain on a 100mm visual analog scale, amount of pain medication used, number of dressings used, quality of life, and number of work/school days lost will also be quantified. Wound site exudate will be graded based on the Table 4 below. HS lesion erythema will be graded on the Clinical Erythema Assessment (CEA) scale (Table 5) at each visit. Active range of motion in degrees of the nearby joint (shoulder or hip) will be observed and recorded using a goniometer in the following directions: flexion, extension, abduction, internal and external rotation (Table 6). During the first and last visit quality of life will be assessed utilizing the Dermatology Life Quality Index (DLQI) and the HS Quality of Life Questioner (HiSQOL). The DLQI questionnaire is designed for use in adult participants with inflammatory skin diseases and has been used in HS studies. The DLQI surveys participants about symptoms and feelings, daily activities, leisure, work and school, personal relationships and treatment. The DLQI total score ranges 0 -30 (lower scores indicating higher health related QOL). A total score of 0 or 1 indicates no significant impact of the disease on health related QOL. A 4 point change in the DLQI total score has been reported to be a meaningful change in the subject's QOL. The HiSQOL questionnaire is comprised of 17 items and has a recall period of 7 days. The HiSQOL includes 3 subscales: symptom status, psychosocial impact, and impact on physical activities. It has been recently validated and is HS disease specific.

At the last visit, the lesion will be swabbed, and the sample will be collected per the tissue collection protocol above. The patient will then be offered excision of the lesion and that tissue will be collected and sent to the lab, as well.

Data and specimens can be accessed by approved study personnel only.

Table 1: HS PGA Scale

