#### 22) Local Number of Subjects

We plan to complete the study on 12 subjects. Given the usual attrition rate we will plan to consent up to 15 subjects.

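### Does the missing look-back period for medication at the first visit undermine the before/after 16S endpoint?

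*Protocol*

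**What the plan says.** Section 7 of the Protocol defines the primary endpoint as the difference in the tunnel microbiome between baseline and the end of 4 weeks on the gel, "as measured by quantitative 16s rDNA PCR for bacterial enumeration". Section 11 calls the study small and unblinded, and no comparator group is described. Section 22 gives the size: "We plan to complete the study on 12 subjects", with up to 15 consented.

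Section 3 has four inclusion and four exclusion criteria. They cover age, diagnosis, a qualifying tunnel ("Have at least one HS related tunneling wound that is at least 2 CM in length"), consent, pregnancy, prisoners and ability to apply the gel at home ("Subjects, who in the opinion of the PI, cannot comply with home application of the treatment"). None mentions antimicrobial use.

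For the first visit, Section 8 says that "concomitant medications will recorded using the medical chart and history given by the patient". The table of assessments in that section also ticks chart review, HS history and medical history at this visit, and ticks concomitant medication at all three visits. None of these rows carries a time window. Two other items do: pain medication covers the previous 3 days, and the HiSQOL "has a recall period of 7 days".

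**The concern.** Without a comparator, anything that changes bacterial load between the two samples is read as part of the treatment effect. Background therapy that stays the same is present at both samples and largely cancels; starts, stops and changes do not. Those that occur between the first and final visits should appear in the medication record, which is taken at every visit.

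The exposed period is just before the first visit. A course that ended a few days earlier is not, read strictly, a concomitant medication, so whether it is written down could depend on who takes the history and how full the chart is. If that course had suppressed the baseline count, recovery by week 4 would offset a true reduction. An analyst cannot set aside courses that were never recorded. The worry is plausible in this population: Section 2 describes standard care as a mix of medical and surgical treatment, and Section 5 recruits from routine clinics. A suppressed baseline would also weaken the evidence for hypothesis H1, which rests on microbial identification and enumeration.

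**Working it through.** The protocol gives no figure to reproduce here: no antimicrobial rate, no SD of change, no test and no power. The only arithmetic it allows is the implied attrition, 1 - 12/15 = 20%. The rest is illustration on stated assumptions.

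**Inputs.** From Section 22: n = 12 completers. Assumed: true change -1 log10; SD of change 1 log10 (0.5 as an alternative); each affected subject rebounds by s = 1 or 2 log10; two-sided 5% t-based inference on the mean change.

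**Step 1: shift in the mean.** With m affected subjects the mean change moves toward zero by m × s / 12.
- m = 1: 1/12 = 0.08 and 2/12 = 0.17 log10.
- m = 3: 3/12 = 0.25 and 6/12 = 0.50 log10.

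**Step 2: power.** With no rebounders, the noncentrality is (1/1) × √12 = 3.46 on 11 degrees of freedom, and power is 88%. Simulating exactly m rebounders gives:

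| m | s | mean change | power, SD 1 | power, SD 0.5 |
|---|---|---|---|---|
| 1 | 1 | -0.92 | 80% | 100% |
| 1 | 2 | -0.83 | 64% | 98% |
| 2 | 1 | -0.83 | 70% | 100% |
| 2 | 2 | -0.67 | 35% | 69% |
| 3 | 1 | -0.75 | 58% | 98% |
| 3 | 2 | -0.50 | 15% | 19% |

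A noncentral-t approximation that inflates the variance to 1 + s²p(1 - p), with p = m/12, gives 80%, 63%, 69%, 39%, 59% and 22% for the SD 1 column. The two methods part most in the last row, where the approximation is roughest.

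**Step 3: what recording would buy.** Take the worst row (m = 3, s = 2). Each rebounder then shows a change of -1 + 2 = +1. If k of the three are recorded and set aside, the mean of the rest is [9 × (-1) + (3 - k) × 1] / (12 - k). For k = 0, 1, 2, 3 that is -0.50, -0.64, -0.80 and -1.00, with power 15%, 27%, 48% and 75% at SD 1. The price is precision: the 95% half-width goes from 2.201/√12 = 0.64 SD with 12 subjects to 2.306/√9 = 0.77 SD with 9.

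This gain belongs to a reduced analysis that could only be supportive, because it drops subjects on a non-random feature. Requiring both the full and the reduced interval to lie below zero gives 35% (m = 2) and 15% (m = 3) at s = 2, no better than the full analysis alone.

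**Step 4: is the information actually missing?** Four rows at the first visit bear on recent treatment: chart review, HS history, medical history and concomitant medication. The narrative names both the chart and the patient as sources. No history row has a window, so the medication row is not an outlier among them. The two items that do have one are repeated measurements whose recall period is part of their definition; the HiSQOL period belongs to the questionnaire. They do not show that a window was intended for medication history and forgotten.

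**The case for a change.** The best case for changing the plan is that a look-back window is a rule for data collection, not for analysis. If the question is not asked in the same way of every subject at the first visit, no analysis plan can recover the answer reliably, and a null result in 12 subjects could not be told apart from masking. The cost would be one dated question, with no effect on eligibility or treatment.

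Part of this stands. The protocol is silent on the window, the direction of bias is right, and a site would do well to ask for dates. But the argument needs the existing chart review and histories to miss recent courses, and to miss them unevenly, and nothing in the document shows that. How far back to ask is the kind of detail set in case report form instructions; Sections 11 and 13 refer to such a form, which is not at hand. Recording a course would make the bias visible without removing it, so the primary comparison would be read as before. The other before/after influences (incision and drainage, the punch incisions such as "A second punch incision will be made at the end of the tunnel", dressings, and regression to the mean) would remain in either case.

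**Conclusion.** No change to the plan is needed. The protocol omits an operational detail; it does not state anything wrongly or contradict itself. Study staff taking an HS history from chart and patient can be expected to fill the gap sensibly, and a supportive analysis that sets aside subjects with recent courses is ordinary content for an analysis plan that is not shown here.

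On assumed values, one affected subject in 12 costs 0.08 to 0.17 log10 of the mean change, and power goes from 88% to 80% or 64% at SD 1, or stays at 98% or more at SD 0.5. The severe losses, down to 15% to 19%, need three of 12 subjects each to rebound by 2 log10 against a true effect of 1 log10. None of those inputs comes from the protocol. In every case the error is toward missing an effect, not toward claiming one. The opposite error, from antimicrobials started during the 4 weeks, is a separate matter that the medication record at all three visits already covers.

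The conclusion rests on the first-visit histories being taken as scheduled. It would be worth revisiting only if the case report form turned out to restrict the medication question to current use.

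### Does listing ESR among serum markers, with only serum collection scheduled, mean that this marker cannot be measured?

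*Protocol*

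**What the plan says.** Section 7 of the protocol sets out a primary endpoint, a set of secondary outcomes, and then a third group introduced as "Other descriptive measures included". The last item in that third group is "Change from baseline in serum levels of markers of inflammation". It is followed by a list of examples that ends with "C-reactive protein (CRP) and erythrocyte sedimentation rate (ESR".

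Section 8 states that "The procedures involved are listed in the table of assessments". The one row of that table that concerns blood is "Serum collection", marked at week 0 and week 4. The narrative in Section 8 describes swabs, punch tissue and an offered excision at the last visit. It does not describe a blood draw of any kind: not the venepuncture, the tubes or the processing. Sections 9 and 20 say that specimens are kept frozen at -80°C.

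**The concern.** An erythrocyte sedimentation rate needs erythrocytes. It is read on whole blood, and serum is what remains once the cells and the clot have been removed. Section 7 therefore attaches ESR to a specimen on which it cannot be measured, and the schedule in Section 8 appears to repeat the error by naming serum alone. No other section mentions a whole-blood sample, and frozen storage would not suit a test that depends on intact cells.

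The worry is about the baseline. A change from baseline needs a value taken before treatment starts at the first visit. If staff drew serum only, that value could not be recovered later, and no analysis method could replace it. The markers serve the third hypothesis in Section 1, that treating the biofilm alters the systemic host response, so a stated aim of the study is touched.

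**Working it through.** The protocol gives no sample size, power or error-rate figure that bears on this point, so there is nothing to reproduce. The check is a count of what is affected, followed by a reading of the sections against each other.

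**Count of markers.** Section 7 names IL-6, IL-8, IL-10, IL-17α, sTNF-RII, CRP and ESR, which makes 7. Six of these can be measured in serum. ESR cannot. The share affected is 1 of 7, which leaves 7 − 1 = 6.

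**Count of endpoints.** The primary endpoint is bacterial enumeration by quantitative PCR. The secondary outcomes are clinical severity, pain, erythema, exudate, range of motion, medication use, work or school days lost, dressings and quality of life. None uses a blood marker, so 0 primary and 0 secondary endpoints are affected.

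**Status of the list.** The markers are introduced as examples, under descriptive measures. Dropping one example would not break a stated endpoint.

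**Does the missing row show that no whole blood will be drawn?** This would follow only if the table listed every sample, and it does not. For the first visit, Section 8 says "The first swab of the lesion will be performed and placed in a collection tube". For the final visit it says "At the last visit, the lesion will be swabbed". Swabbing has no row in the table. Nor do the local anaesthesia and the probing of the tunnel, both described in the same section. A procedure can therefore be intended and described in this protocol without a row of its own, and the absence of a whole-blood row carries little weight.

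**Does the storage wording rule it out?** Section 9 concerns banking and Section 20 the research laboratory and setting. Neither says where or how ESR would be run. The sentence on frozen storage describes what happens to kept specimens. It does not address a test done on the day and then discarded.

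**What would have to happen for data to be lost?** Someone would have to read the word serum so strictly that no whole blood was taken for a test whose name refers to red cells. A laboratory asked for an ESR would call for a whole-blood tube. Blood is already drawn at the two visits where ESR is wanted, so the tube adds no visit and no further venepuncture.

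**Can the loss be given a number?** Only as a ceiling. Section 22 states "We plan to complete the study on 12 subjects", with up to 15 consented. If every subject were missed there would be no paired ESR change in any of the 12 and no baseline in any of the 15. Those figures are simply the planned enrolment under total failure. Nothing in the protocol makes that outcome likely, so they are not an estimate of the loss.

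**The case for a change.** The best case for a change is that the choice of specimen belongs in the protocol. An analysis plan can specify a model later, but it cannot restore a tube that was not filled before treatment. Three places lean the same way: the endpoint wording says serum, the schedule says serum, and the storage sections describe freezing. Correcting the text would be cheap: name whole blood beside serum at the two existing draws, or drop ESR and keep CRP. On this view a cheap correction that guards against an unrecoverable baseline is worth asking for.

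Part of this stands. ESR is misdescribed as a serum level, no section names the specimen it needs, and a baseline that is missed stays missed. An author revising the protocol for other reasons could tidy the wording.

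The step from loose wording to lost data does not stand. The protocol states plainly that ESR is wanted, it goes into no detail on how any blood is drawn, and its table omits other samples that will certainly be taken. Tube type for each test is the kind of detail that a laboratory manual or the site's own routine supplies. Even if the worst happened, an illustrative descriptive marker would be missing while CRP, the other routine inflammation marker in the list, would still be measured in the scheduled serum.

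**Conclusion.** The mismatch between ESR and serum is genuine but clerical, and no change to the plan is called for. It concerns 1 of 7 example markers in a descriptive group, with 0 primary and 0 secondary endpoints affected. Six markers, CRP among them, remain for the hypothesis about systemic response. No sample size, analysis or conclusion would differ once the wording was corrected.

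This rests on two assumptions. The first is that serum is used here as shorthand for the blood draw, which is the natural reading given that ESR is named. The second is that staff or the laboratory will fill a whole-blood tube at the existing venepunctures at week 0 and week 4. The protocol neither states nor contradicts the second. If it failed completely, the study would lose one descriptive marker and nothing that it sets out as a primary or secondary outcome.
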